8.2.7 Safety Laboratory Parameters

Safety laboratory parameters which are to be taken at every visit to the clinic:

- Haematology: Haemoglobin (Hb), haematocrit (erythrocyte volume fraction), platelet count (thrombocyte particle concentration [TPC]), leucocyte count, mean corpuscular volume (MCV)
- Biochemistry: Albumin, alanine transferase (ALT), aspartate aminotransferase (AST), alkaline phosphatase (ALP), bilirubin, blood urea nitrogen (BUN), calcium, creatinine, c-

Clinical Trial Protocol

Vicore Pharma AB
Trial ID: VP-C21-005

Version: 7.0
Date: 15-Sep-2021

reactive protein (CRP), gamma glutamyl transferase (GGT), glucose, lactate dehydrogenase (LD), potassium, sodium

- Urinanalysis: Dipstick for bilirubin, glucose, ketones, protein, specific gravity, urobilinogen, and pH

Any laboratory abnormality, judged by the investigator to be a clinically relevant worsening since Visit 1, should be reported as an AE if the laboratory abnormality requires clinical intervention or further investigation, unless the laboratory abnormality is associated with an already reported event.

8.3 Other Assessments

8.3.1 Demographics and other Baseline Characteristics

Demographic and baseline characteristics include but are not limited to age at screening, sex, height, and weight.

8.3.2 Slit Lamp Examination

A slit lamp examination will be performed by an ophthalmologist prior to Visit 2 and at Visit 15, where the results in the form of a written report including acuity, lens state, and any contraindications to cataract surgery will be reviewed by the investigator. The conduct of the slit lamp examination could be delegated to a registered optometrist, provided that the report is reviewed and approved by an ophthalmologist.

Each slit lamp examination will be reported as “normal”, “abnormal – non clinically significant” or “abnormal –clinically significant”. Any clinically significant abnormalities prior to initiation of IMP should be specified and recorded as medical history. New clinically significant abnormalities occurring after initiation of IMP should be reported as AEs.

Clinical Trial Protocol

9 ADVERSE EVENTS

9.1 Adverse Event Definitions

An adverse event (AE), an adverse drug reaction (ADR) and a serious adverse event (SAE) are defined according to ICH Guideline E2A ([ICH 1994](#)).

An AE is any untoward medical occurrence in a subject administered the IMP and which may or may not have a causal relationship with this IMP. An AE can therefore be any unfavorable and unintended sign (e.g. a significant abnormal laboratory finding, symptom, or disease temporally associated with the use of the IMP, whether or not considered related to the IMP).

An ADR is any noxious and unintended response to an IMP related to any dose of the IMP.

An SAE is any untoward medical occurrence that at any dose:

- Results in death
- Is life-threatening (this refers to an event in which the subject was at risk of death at the time of the event; it does not refer to an event that hypothetically might have caused death if it was more severe)
- Requires in-patient hospitalisation or prolongation of existing hospitalisation
- Results in persistent or significant disability or incapacity
- Is a congenital anomaly or birth defect
- Is judged medically important (this refers to an event that may not be immediately life-threatening or result in death or hospitalisation, but may jeopardise the subject or may require intervention to prevent one of the other outcomes listed)

A non-SAE is any AE that does not meet the definition of an SAE.

The following will not be considered an AE:

- Pre-planned procedure (documented at Visit 1) unless the condition for which the procedure was planned has worsened from the first trial related activity after the subject has signed the informed consent form
- Concomitant illness identified as a result of screening procedures. However, if symptoms are worsened and/or become serious as defined in Section 9.1, this must be reported as a SAE.

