9.2 Adverse Event Assessment Definitions

9.2.1 Severity

The investigator should assess the severity of all AEs according to the following definitions:

- Mild: awareness of sign or symptom, but easily tolerated (acceptable).
- Moderate: discomfort to interfere with usual activities (disturbing).
- Severe: incapacity to work or to perform usual activities (unacceptable).

Clinical Trial Protocol

Vicore Pharma AB
Trial ID: VP-C21-005

Version: 7.0
Date: 15-Sep-2021

Note the distinction between seriousness and severity: The term severe is used to describe the intensity of the event and a severe event is not necessarily serious. The seriousness criteria serve as a guide for defining regulatory reporting obligations.

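### Section 9.1 has no route by which non-serious worsening of an illness found at screening is counted as an ordinary AE, and the examination sections give no rule for worsening

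*Combined protocol and SAP*

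**What the plan says.** Section 9.1 lists six seriousness criteria and then draws the boundary: "A non-SAE is any AE that does not meet the definition of an SAE". It goes on to list what will not count as an AE. The second item is "Concomitant illness identified as a result of screening procedures", followed directly by "However, if symptoms are worsened and/or become serious as defined in Section 9.1, this must be reported as a SAE".

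Section 9.2.1 separates severity from seriousness and adds: "The seriousness criteria serve as a guide for defining regulatory reporting obligations".

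The assessment sections have their own rules:

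- Slit lamp (8.3.2), with the same pattern for physical examination (8.2.4) and ECG (8.2.6): "Any clinically significant abnormalities prior to initiation of IMP should be specified and recorded as medical history", and then "New clinically significant abnormalities occurring after initiation of IMP should be reported as AEs".
- Laboratory (8.2.7): an abnormality "judged by the investigator to be a clinically relevant worsening since Visit 1, should be reported as an AE", on the further condition that it needs clinical intervention or further investigation, and unless it belongs to an event already reported.

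Section 9.3 requires every event that meets the AE definition to be reported from consent to Visit 15. Cardiac and ophthalmic AEs go to the sponsor within 24 hours. The primary endpoint (4.4) is the nature and frequency of adverse events.

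**The concern.** Worsening of a pre-existing condition is a common kind of event in an older population with comorbidity, and a safety endpoint needs one rule for it. Here the ordinary category, a non-serious AE, is missing from the clause in 9.1 that deals with illness found at screening. The examination sections do not supply it, because they speak only to new findings. The laboratory section does supply it, with a condition of its own.

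The trial has one arm, so there is no comparator against which site-to-site differences in classification could balance out. SAEs are reported within 24 hours and are evaluated by the IDMC as they arise, so an event labelled SAE only because of the wording enters that stream. An event left out of the AE definition enters no AE table.

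**Working it through.** The plan gives no figure to reproduce on this point. The check is a comparison of the rules, followed by a statement of scale.

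**Step 1. The two readings of 9.1, applied to a symptomatic, non-serious worsening of an illness found at screening.**

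| Reading of the clause | Result | Consequence |
|---|---|---|
| Literal: worsening alone is enough, because of the and/or | SAE | Conflicts with the six criteria, with the non-SAE definition in 9.1, and with the severity/seriousness distinction in 9.2.1 |
| Charitable: the cross-reference to 9.1 requires a seriousness criterion | Stays under the list of things that are not AEs | The mention of worsening does no work, and the event is not counted |

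Neither row gives an ordinary AE. The item just above it in the same list, on pre-planned procedures, does let worsening of the underlying condition lift the exclusion, so a workable model is already in the section.

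**Step 2. The assessment sections, applied to worsening of a finding present before IMP.**

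| Section | Rule for worsening | Planned summary in 13.4 |
|---|---|---|
| 8.2.4 Physical examination | None stated; names new findings | Abnormal findings by visit (13.4.5) |
| 8.2.6 ECG | None stated; names new findings | By visit and change from baseline (13.4.2) |
| 8.3.2 Slit lamp | None stated; names new findings | None listed |
| 8.2.7 Laboratory | AE if clinically relevant and needing intervention or investigation | By visit and shift table (13.4.4) |

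**Step 3. The case that falls through.** The slit lamp examination is a screening procedure (6.5.1). Take a lens finding rated clinically significant before treatment and recorded as medical history, which has progressed by Visit 15 without symptoms. It is not new under 8.3.2. No symptoms have worsened, so the 9.1 clause is not triggered. It was already in the highest of the three reporting categories, so its category does not change. No slit lamp summary is listed that would show it. The 24-hour rule for ophthalmic AEs starts only once somebody calls it an AE.

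**Step 4. Scale.** One subject moved between serious and non-serious, with no other SAE, in a safety set of 60: 1/60 = 1.7 percentage points of SAE incidence. Withdrawals before week 12 are replaced, so the safety set may exceed 60 and the step would then be smaller.

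The documents give no rate of non-serious worsening. Assuming a proportion p of 60 subjects, the expected number is 60p and the chance of at least one is 1 − (1 − p)^60:

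| Assumed p | Expected subjects | Chance of at least one |
|---|---|---|
| 2% | 1.2 | 70% |
| 5% | 3 | 95% |
| 10% | 6 | 99.8% |
| 20% | 12 | >99.9% |

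These show only that the situation is likely to arise at least once over the assumed range. They do not estimate a bias.

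**The case against.** A reader might infer several stronger things, and the documents do not support them.

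- *SAE counts are inflated.* That would follow only if sites applied the literal reading. The reference to the definitions in 9.1 allows the other reading. Inflation is possible but not shown.
- *The examination sections report only new findings and so contradict 9.1.* They do not say only, and they exempt nothing. They are silent on worsening. The general AE definition in 9.1 and the reporting duty in 9.3 remain, and an investigator may report a progression under them. This backstop is real but partial: 9.3 covers what meets the AE definition, and the 9.1 list takes illness found at screening out of it.
- *Aggravation of heart findings is hidden.* Clinically significant resting ECG abnormalities at Visit 1 are exclusionary (5.2, criterion 9). Section 8.2.6 has no three-level category in which a finding could stay put, and ECG changes from baseline are tabulated whatever their AE status. A finding that becomes clinically significant on treatment can also be read as new. What is left on the cardiac side is mainly the new-findings wording of 8.2.4, which covers the cardiovascular examination at Visits 3-14.
- *Misfiled SAEs change the urgency of eye and heart events or trigger expedited reporting.* Cardiac and ophthalmic AEs go to the sponsor within 24 hours whether serious or not, and expedited reporting to authorities is for SUSARs, not all SAEs.

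The 9.1 clause is also narrow. It concerns illness identified by screening procedures, and it speaks of symptoms. On the eye side, exclusion criterion 5 directs attention to serious ophthalmic conditions, and the investigator reviews the Visit 15 report on acuity and lens state. The AE endpoint is descriptive, with no test or threshold. These points limit the consequence. They do not repair the clause, which fails on both readings.

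**Conclusion.** The point holds as a drafting defect in the rules that feed the primary endpoint. Section 9.1 never classifies non-serious worsening of a screening-identified illness as an ordinary AE, and the protocol treats worsening differently in 9.1, in 8.2.7, and (by silence) in 8.2.4, 8.2.6 and 8.3.2. Classification can therefore depend on which section a site follows. The main practical gap is symptom-free progression of an already clinically significant slit lamp finding.

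The size of the effect cannot be derived from the documents. The only firm figure is the step of about 1.7 percentage points in SAE incidence per reclassified subject, which assumes a safety set of 60 and no other SAE in that subject. The proportions tabulated above are assumptions. Severity: should-fix.

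**What to change.** - In 9.1, replace the closing sentence of the item on screening-identified illness with a rule to this effect: *worsening of such a condition after consent is reported as an AE, and as an SAE only if it meets one of the seriousness criteria listed above.*
- In 8.3.2, and for consistency in 8.2.4 and 8.2.6, extend the reporting sentence beyond new findings by adding: *or clinically significant worsening of a pre-existing abnormality.* The laboratory rule in 8.2.7 carries an extra condition (intervention or further investigation). The sponsor should decide whether that difference is intended.

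A slit lamp shift table alone would not close the gap, because a finding already in the top category would show no shift.

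The cost is four sentences in an amendment and matching text in the eCRF completion guide. A few more non-serious AEs will be reported. No procedure is added and no treatment rule changes.

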9.2 Adverse Event Assessment Definitions

9.2.1 Severity

The investigator should assess the severity of all AEs according to the following definitions:

- Mild: awareness of sign or symptom, but easily tolerated (acceptable).
- Moderate: discomfort to interfere with usual activities (disturbing).
- Severe: incapacity to work or to perform usual activities (unacceptable).

Clinical Trial Protocol

Vicore Pharma AB
Trial ID: VP-C21-005

Version: 7.0
Date: 15-Sep-2021

Note the distinction between seriousness and severity: The term severe is used to describe the intensity of the event and a severe event is not necessarily serious. The seriousness criteria serve as a guide for defining regulatory reporting obligations.

9.2.2 Relationship to IMP

Assessment of causality is based on the following considerations: associative connections (time and/or place), pharmacological explanations, previous knowledge of the drug, presence of characteristic clinical or pathological phenomena, exclusion of other causes, and/or absence of alternative explanations.

The investigator will be asked to assess causal relationship to the trial treatment according to the following classifications:

Related:

- Time relationship exists; and previous knowledge of the trial product supports a causal relationship although another cause cannot be ruled out; and/or improvement on dechallenge or dose reduction has occurred (if performed); and/or recurrence of symptoms on rechallenge has occurred (if performed); and/or a specific laboratory test supports a causal relationship

Not related:

- No time relationship between administration of the trial product and occurrence or worsening of the AE exists; and/or another cause is confirmed and no indication for involvement of the trial product in the occurrence/worsening of the AE exists. The alternative, most likely other cause(s) should be indicated

9.2.3 Outcome

The investigator will be asked to record the most appropriate outcome of the following:

- Recovered
- Ongoing
- Not recovered
- Recovered with sequelae
- Death
- Unknown

9.3 Reporting of Adverse Events

All events meeting the definition of an AE must be reported in the period from the subject has signed the informed consent form until the end of trial participation (Visit 15).

At each visit the subject will be asked about AEs in an objective manner, e.g.: “Have you experienced any problems since the last visit?”

Only medically qualified personnel (investigators) must assess AEs.

Clinical Trial Protocol

Vicore Pharma AB
Trial ID: VP-C21-005

Version: 7.0
Date: 15-Sep-2021

AEs must be reported on the AE form. In the eCRF the diagnosis should be recorded, if available. If no diagnosis is available each sign and symptom should be recorded as individual AEs.

AEs concerning cardiac or ophthalmic conditions are of special interest and must be reported to the Sponsor within 24 hours of obtaining knowledge of the event.

SAEs, in addition, must be reported within 24 hours of obtaining knowledge of the event. The information to be reported will include assessment of severity, causal relationship to IMP or trial procedures, action taken, outcome, and a narrative description of the course of the event. Additional information may be subsequently provided.

The SAE form and all other relevant documents supporting the reported SAE (e.g. diagnostic procedures, hospital records, autopsy reports) must be faxed or scanned/mailed to the Sponsor or Sponsor's designee.

The independent ethics committees (IEC) and regulatory authorities will be notified of SAEs according to current regulation and local requirements.

All suspected unexpected serious adverse reactions (SUSARs) are subject to expedited reporting to regulatory authorities.

The expectedness of a SUSAR will be assessed against the reference safety information. Any SUSARs will be reported by the clinical research organisation (CRO) to the relevant competent authority. SUSARs will also be reported to the IEC by the site/CRO. Fatal and life threatening SUSARs will be reported as soon as possible and no later than seven calendar days from the date of first knowledge of the event. Relevant follow-up information will subsequently be expedited within an additional eight days. All other SUSARs will be expedited no later than 15 calendar days of first knowledge of the event.

For AEs concerning hair symptoms, additional information may be collected, such as location and extent of hair loss, outcomes of dermatologist consultations, results from special investigations, and any photographs taken.

9.4 Follow-up on Adverse Events

All AEs should be followed until they are resolved or the subject's participation in the trial ends, whichever comes first.

SAEs and non-serious AEs considered related to trial drug should be followed on a regular basis according to the investigator's clinical judgment until a final outcome has been established.

9.5 Pregnancies

Any pregnancy that occurs during trial participation must be reported and administration of trial drug must be terminated immediately. A pregnancy must be reported to Sponsor or designee within 2 weeks of learning of its occurrence. The pregnancy must be followed up to determine outcome (including premature termination) and status of mother and infant. Pregnancy complications and elective terminations for medical reasons must be reported as AEs or SAEs, as applicable. Spontaneous abortion must be reported as an SAE.

Clinical Trial Protocol

Vicore Pharma AB
Trial ID: VP-C21-005

Version: 7.0
Date: 15-Sep-2021

In addition, the investigator must attempt to collect pregnancy information on any female partners of male trial participants who become pregnant while the participant is enrolled in the trial. Pregnancy information must be reported to Sponsor as described above.

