5.3 Restrictions During the Trial

5.3.1 Contraception Requirements

Women of child bearing potential must practice abstinence (if that is their preferred lifestyle) from Visit 1 to Visit 15, or must agree to use a highly effective method of contraception with a failure rate of <1% to prevent pregnancy (combined [oestrogen and progestogen containing] hormonal contraception associated with inhibition of ovulation [oral, intravaginal, transdermal], progestogen-only hormonal contraception associated with inhibition of ovulation [oral, injectable, implantable], intrauterine device or intrauterine hormone-releasing system) from at least 4 weeks prior to first IMP administration to 4 weeks after last IMP administration. Their male partner must agree to use a condom during the same time frame, unless he has had a demonstrated successful vasectomy more than 6 months prior to first IMP administration.

Males should use condom and their female partner of child-bearing potential must use a contraceptive method with a failure rate of <1% to prevent pregnancy (see above) and drug exposure of a partner and refrain from donating sperm from the date of dosing until 3 months after the last IMP administration.

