6 TRIAL DESIGN

6.1 Overall Trial Design

This is a multi-centre, open-label, single-arm trial investigating the safety and efficacy of C21 in which subjects with IPF will be treated for a maximum of 36 weeks. In total, approximately 60 subjects will be recruited.

To ensure careful and ongoing evaluation of the individual risk/benefit profiles, each subject will undergo a medical evaluation by the investigator at the end of every 12-week treatment period, where the investigator will evaluate if continuation into the next 12-week treatment period is considered safe for the individual subject.

In addition, throughout the duration of the trial, an independent data monitoring committee (IDMC) will evaluate all serious adverse events (SAEs) on an ongoing basis in accordance with the IDMC charter. The IDMC will monitor all available safety data during regular meetings as

Clinical Trial Protocol

Vicore Pharma AB
Trial ID: VP-C21-005

Version: 7.0
Date: 15-Sep-2021

defined in the IDMC charter and provide appropriate recommendations to the Sponsor on the overall safety of trial participants (see Section 14).

The subjects will attend up to 15 visits to the clinic:

- Visit 1: Screening
- Visits 2 – 7: Treatment period 1
- Visits 8 – 11: Treatment period 2
- Visits 12 – 14: Treatment period 3
- Visit 15: End-of-trial

IMP will be administered as home treatment twice daily (*b.i.d.*) during all treatment periods 1-3.

Final safety follow-up assessments at Visit 15 (end of trial visit), must be performed for all subjects who have received trial treatment. Visit 15 must be scheduled 2-4 weeks after the last IMP administration (see Section 7.3).

The maximum duration of the trial for any subject will be approximately 44 weeks, including a screening period of up 4 weeks, a treatment period up to 36 weeks and a visit for safety follow up to be conducted maximum 4 weeks after the last dose of IMP (please see clinical trial design in Figure 1).

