6.5.3 End-of-Trial (Visit 15)

Visit 15 is performed minimum 2 weeks and maximum 4 weeks after the last IMP administration.

The following procedures are performed:

- Recording of concomitant medication
- 12-lead ECG
- Blood sampling for safety and biomarker assessments (See [Table 1](#) and Section [8](#))
- Urinalysis
- Pregnancy test (beta-HCG)
- Physical examination including body weight (See [Table 1](#) and Section [8.2.4](#))
- Vital signs
- Spirometry
- Slit lamp examination
- Concomitant medication
- Reporting of AEs

If a subject is withdrawn from treatment (see Section [5.7](#)), a Visit 15 (end-of-trial visit) must be performed.

Clinical Trial Protocol

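### Section 9.5 stops collecting new partner pregnancies at Visit 15, 9 to 11 weeks before the male precaution period in Section 5.3.1 ends

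*Combined protocol and SAP*

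**What the plan says.** **Precautions (Section 5.3.1).** Male subjects are to use a condom, have a partner of childbearing potential use effective contraception, and "refrain from donating sperm from the date of dosing until 3 months after the last IMP administration". Women who rely on contraception continue it "from at least 4 weeks prior to first IMP administration to 4 weeks after last IMP administration". Women who practise abstinence do so from Visit 1 to Visit 15.

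**Collection (Section 9.5).** For subjects, the rule is "Any pregnancy that occurs during trial participation must be reported". For male subjects, the investigator must try to obtain information on "female partners of male trial participants who become pregnant while the participant is enrolled in the trial". Reports are due within 2 weeks of learning of the pregnancy. Each reported pregnancy is followed to its outcome, and no stop at Visit 15 is stated for that follow-up.

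**End of participation.** Sections 8.2.1 and 9.3 place the end of trial participation at Visit 15. Section 6.5.3 says "Visit 15 is performed minimum 2 weeks and maximum 4 weeks after the last IMP administration". Section 5.7 requires the same visit for withdrawn subjects. No contact is scheduled after it.

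**The concern.** The protocol asks men to avoid conception for three months after dosing ends, yet its rule for collecting partner pregnancies appears to end much sooner. A partner pregnancy that begins 6 or 10 weeks after a man's last dose lies inside the sponsor's own precaution period and outside the collection rule. A site following Section 9.5 to the letter would have no duty to ask about it or report it.

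At stake is safety information on pregnancies with possible drug exposure. Section 3.7 describes this as the first trial in which patients receive repeated doses of C21, so each such case would be informative. Section 9.5 treats spontaneous abortion as a serious event, and Section 9.1 lists congenital anomaly as a seriousness criterion. A report stating that no partner pregnancies occurred would not cover the last 9 to 11 weeks of the period the sponsor chose to guard.

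**Working it through.** **Inputs**
- Visit 15: 2 to 4 weeks (14 to 28 days) after the last dose (Section 6.5.3; Table 1, footnote 1).
- Male precautions after the last dose: 3 months (Section 5.3.1). I take this as 91 days (13 weeks), with 84 days (12 weeks) as a lower check.
- Female contraception after the last dose: 4 weeks, or 28 days (Section 5.3.1).
- Longest treatment: 36 weeks, or 252 days (Section 6.1).

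**The plan's own figure.** Section 6.1 states: "The maximum duration of the trial for any subject will be approximately 44 weeks". Its parts are 4 weeks of screening, 36 of treatment and at most 4 of follow-up: 4 + 36 + 4 = 44 weeks. This reproduces, and it confirms that participation ends no later than 4 weeks after the last dose.

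**Gap for men** = precaution period after last dose − time from last dose to Visit 15.

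| 3 months taken as | Visit 15 at week 4 | Visit 15 at week 2 |
|---|---|---|
| 91 days | 91 − 28 = 63 days (9 weeks); 63/91 = 69% | 91 − 14 = 77 days (11 weeks); 77/91 = 85% |
| 84 days | 84 − 28 = 56 days (8 weeks); 56/84 = 67% | 84 − 14 = 70 days (10 weeks); 70/84 = 83% |

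**The same gap against the whole male period.** Male precautions start with dosing. For a man treated for 36 weeks the period is 252 + 91 = 343 days (49 weeks). The uncollected share is 63/343 = 18% to 77/343 = 22%. With shorter treatment the share is larger: after 12 weeks (84 days) it is 63/175 = 36% to 77/175 = 44%.

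**Gap for women using contraception.** 28 − 28 = 0 days to 28 − 14 = 14 days. Table 1 places Visit 15 at week 40, 4 weeks after the week-36 visit, so the gap at the scheduled time is 0. For women practising abstinence, precaution and collection both end at Visit 15.

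**Does another provision close the gap for men?** Three come close:
- The outcome follow-up in Section 9.5 applies to pregnancies already within its collection rule.
- The infant follow-up in Section 5.7 applies to subjects withdrawn because of pregnancy.
- Section 9.4 follows serious and related events already recorded.

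None brings in a partner pregnancy that begins after Visit 15.

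**The case against.** **The sections do different jobs.** Section 5.3.1 is a precaution and Section 9.5 is a reporting rule. The protocol never says that their end dates must match. This stands: it is a design gap, not a strict contradiction. But the rule followed exactly still misses exposures that the precaution was meant to prevent.

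**The wording is loose.** Section 9.5 does not define enrolment. In Section 5.3.1 the three-month limit could be read as attached only to sperm donation. Both points are fair. The wider reading is the natural one, because no other end date is given for men's contraception. If the sponsor meant enrolment to last beyond Visit 15, Section 9.5 needs to say so.

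**Stronger readings that the documents do not support.** A reader might infer any of the following:
- *Most of the male precaution period is uncollected.* That is true only of the three months after the last dose. All time on treatment and the first 2 to 4 weeks after it are covered, which is roughly four fifths of the whole period for a man treated for 36 weeks.
- *Outcomes after Visit 15 are lost.* Section 9.5 follows a pregnancy that began before Visit 15 to its outcome, whenever that falls. One recognised only after Visit 15 does, however, depend on unprompted reporting.
- *Women face the same gap.* Theirs is zero at the scheduled visit and at most 2 weeks.
- *The primary endpoint is compromised.* That endpoint is adverse events over the trial period (Section 4.4), and Section 9.1 defines an adverse event as occurring in a subject given the IMP. A partner pregnancy beginning after Visit 15 is neither.

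**Few cases are likely.** Subjects are aged 40 or over, and Section 3.1 puts typical symptom onset between 50 and 70 years. The protocol gives no pregnancy rate and does not say how many men have a partner of childbearing potential. This limits the practical weight of the point but does not remove it.

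**Conclusion.** The gap is real and narrow. Partner pregnancies that begin in the last 9 to 11 weeks of the male precaution period fall outside the collection rule (8 to 10 weeks if three months is counted as 12 weeks). The percentages depend on the denominator and should be quoted with it: 69% to 85% of the three months after the last dose, or 18% to 22% of the 49-week period for a man treated for 36 weeks.

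This rests on two readings: that enrolment in Section 9.5 ends with participation at Visit 15, and that the three-month limit covers men's contraception as well as sperm donation. The number of missed cases cannot be estimated from the documents and is probably small. The sample size, the FVC analysis and the primary adverse event summary are untouched. It is a worthwhile, inexpensive improvement to safety data collection. The length of the precaution periods is not in question.

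**What to change.** Reconcile Section 9.5 with Section 5.3.1. State in 9.5 that pregnancies, chiefly those in partners of male subjects, are collected until the matching period in 5.3.1 ends, including after Visit 15. Define enrolment for this purpose, and make clear in 5.3.1 which male precautions the three-month limit governs. At the existing Visit 15, and in the subject information, ask subjects to report any such pregnancy to the site. Apply the 2-week reporting limit and outcome follow-up already in 9.5.

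**Cost.** About one sentence in 9.5, a clarification in 5.3.1 and a subject-information update that needs ethics review. If the change counts as substantial, Section 10.1 requires approval before it is implemented. No visit, sample or procedure is added. Reports after Visit 15 would be passive, so some cases could still be missed. A late report might arrive after database lock and would then be handled through the safety database without reopening the trial data.
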